	9.3	CONFIDENTIALITY	
	9.4	INDEMNITY	
	9.5	Sponsor	
	9.6	Funding	
	9.7	Audits	
10		UDY MANAGEMENT	
11	L PUE	BLICATION POLICY	16
12	2 REF	FERENCES	17

CSP: Conduction system pacing CT: Computed tomography ECG: Electrocardiogram

EGG. Electrocardiogram
EGM: Electrogram
HBP: His-bundle pacing
ICE: Intracardiac echocardiogram
LBBB: Left bundle branch block LBP: Left bundle pacing
LBAP: Left bundle area pacing
LV: Left ventricle
LVAT: Left ventricular activation time

MRI: Magnetic resonance imaging

RV: Right ventricle

TOE: Transoesophageal echocardiogram TTE: Transthoracic echocardiogram

Study Summary

TITLE	Fluoroless Conduction System Implant		
DESIGN	Cohort observational study and interventional at validation phase		
AIMS	Define a feasible fluoroless protocol for conduction system lead implantation		
	Primary Outcomes:		
OUTCOME MEASURES	1. Success rate of conduction system lead implant Secondary Outcomes: 2. Fluoroscopy time 3. Total procedure time 4. Capture threshold 5. Number of times leads deployed 6. Complication rates: a. Lead implanted at the incorrect position: non-septal positions b. Lead displacement c. Lead injury d. Rise in threshold (late complication) e. Vascular injury f. Perforation with or without subsequent tamponade g. Device related infection h. Pneumothorax		

POPULATION	Patients with any indication for a pacemaker
ELIGIBILITY	Main Inclusion Criteria 1. Patients with a ventricular pacing indication: high grade atrioventricular block and symptomatic trifasicular or bifasicular block. (in order to assess the level of conduction system block) 2. Adults willing to take part (ages 18 – 100 years old) 3. Able to give consent.
	Main Exclusion Criteria 1. Unable to give consent 2. Children age < 18 years and adults > 100 years old 3. Pregnant patients 4. Pacing device in situ 5. Indication for cardiac resynchronisation therapy 5.
DURATION	1 year

1. Introduction

1.1 Background

Discovering how to clinically deliver conduction system pacing efficiently could be a paradigm shift. Early work on conduction system pacing focused on the His bundle, with right atrial mapping for the His signal and deployment of a lumenless pacing lead(1). Left bundle pacing (LBP) then emerged as an alternative, approaching via the basal right ventricular septum to deploy a lead through the septum to capture the left bundle on the left side of the septum(2,3)

Current literature report improved left ventricular function, heart failure outcomes and mortality in conduction system pacing(4,5). Additionally, LBP has a larger target area, can be done with low capture thresholds, has better threshold stability and large amplitude R waves(3). Widespread roll out of conduction system pacing clinically, however, faces three major challenges.

Challenge A1: Identifying target area for lead deployment

Despite growing adoption, conduction system pacing implants remains challenging. Even experienced device consultants take time to learn the technique. Experienced centres achieve implant success of 95%, but centres with new conduction system implanters (but highly experienced pacemaker implanters) have rates as low as 56%(6,7).

Fluoroscopic interpretation is challenging, for several reasons. The target area is smaller than conventional right ventricular pacing, and can be even smaller when there is fibrosis in the septum. The chambers may well be dilated, which displaces not only the fluoroscopic position of the target, but also its orientation. The lead can also be difficult to advance, because of septal fibrosis, unrecognised lead entanglement and unclear trans-septal trajectory. Interpretation of surface ECG and lead data is not straightforward either: there are many levels in the conduction system at which block can occur and it is difficult to distinguish them confidently. Lead entanglement and mal-orientation may be detectable with elaborate equipment such as intracardiac echocardiography (ICE) but we do not know what fluoroscopic or electrical features might provide routine clinical operators with a timely warning. Previous approaches to address these issues have involved normal-heart cadaveric studies which do not give the electrical context of a clinical implant(8).

These challenges can be overcome with visualising the cardiac anatomy that can be achieved with electroanatomical mapping. These 3D mapping systems are also being used to develop fluoroless implant strategies. Cumulative radiation exposure is a well-documented operator risk that has been minimised through various approaches that include personal lead protection, lead shields, image intensifier position, reduced frame rate and short acquisitions (9,10). With the reduction in fluoroscopy time in this study, cumulative radiation exposure to implanters is further reduced through a novel method.

Advances in electroanatomical mapping have allowed fluoroless techniques to have similar procedure times to conventional conduction system implant methods. Fluoroless His-bundle implants have been described in small observational studies, using Abbott's Ensite Precision mapping systems. (11–15)

1.2 Original Hypothesis

- Conduction system leads can be implanted with almost no fluoroscopy using electroanatomical mapping
- 2. Using electro-anatomical mapping will increase safety of conduction system lead implantation
- The procedure times with electro-anatomical mapping will be less than that of conventional methods using fluoroscopy

1.3 Rational for Current Study

Currently conductions system pacing can have long fluoroscopy times when compared to conventional right ventricular pacing. This may be due to difficult cardiac anatomy, altered lead trajectory and obstacles such as entanglement, that is not readily visualised with fluoroscopy. As a result operators experience additional cumulative fluoroscopy times. Our study will devise a standardised implantation protocol using 3D electroanatomical mapping systems to reduce both fluoroscopy and procedure times.

2. Study Objectives

Primary Objective

The primary objective of this study is develop a fluoroless implant protocol of conduction system leads using 3D electroanatomical mapping.

Secondary Objective

The secondary objectives will be

- To reduce the overall procedure and fluoroscopy time with utilisation of targeted lead deployment.
- 2. Improve complication rates

3. Recruitment

A total of 75 patients will be recruited for the study

50 patients with a ventricular pacing indication (high grade atrioventricular block and symptomatic trifasicular or bifasicular block) for pacing will be recruited prospectively. The patients will be divided into two groups; 25 patients in the derivation cohort and 25 patients in the validation cohort. The derivation cohort will undergo a detailed research protocol to determine the optimised work flow and this will be applied prospectively to the validation cohort.

The success rates, procedure times, complication rates and fluoroscopy times will be assessed. The 25 patients undergoing conventional methods of conduction system pacing will be recruited as a control arm to compare these outcomes.

In summary, the 75 patients will be grouped as following; 25 patients in the derivation cohort, 25 patients in the validation cohort and 25 patients in the control arm.

4. Methodology

4.1 Derivation

The derivation cohort will comprise of 25 prospectively recruited patients. These patients will undergo the research protocol. In these patients, we will attempt to implant a permanent conduction system pacing lead, in lieu of the RV or LV lead. The lead will be implanted by operators who have implanted more than 40 leads to overcome the learning curve.

Pre-implant

Prior to the procedure, patients will undergo a clinically indicated Cardiac MRI. We will use these scans to retrospectively assess for the presence of potential mechanisms which could prevent successful lead implantation, such as the presence of septal fibrosis and chamber dimensions, so that we can assess how these can contribute to challenges at the time of implant. We will also be able to review mechanisms for *successful* implants. This information will be corroborated with data collected from the electro-anatomical maps.

The MRI scans will also be used to merge the anatomical information using CartoMerge to reduce procedure times by building the anatomical geometry prior to the mapping-catheter collecting this information invasively.

During Implant

The participants will undergo the following procedural steps after written informed consent is gained:

- A left infraclavicular incision and axillary access for the lead will be gain as per standard clinical protocol.
- 2. Access from the femoral vein will be sought where a sheath will be placed in the femoral vein to introduce the mapping catheter.
- 3. Fast anatomical mapping (FAM) of the right atrial and right ventricular anatomy will be made where CartoMerge has not already created this anatomy. This will include the right ventricle, the tricuspid valve and the right ventricular outflow tract. Activation and voltage maps will be then be made of the His-bundle area (including the His cloud), right ventricle, right ventricular outflow tract and right ventricular septum.

This will help determine a few key aspects

- 1. Level of conduction system block and therefore guide site of lead deployment
- 2. Anatomy of the right heart and overcome challenges this may propose
- 3. Evidence of septal fibrosis and/or scar that need to be overcome
- 4. Activation pattern of the septum in conduction system block
- 4. Anatomical FAM maps, voltage maps and activation patterns will be compared against the data collected from the cardiac MRI to assess
 - 1. Accuracy of anatomy
 - 2. Fibrosis and scar patterns

The CartoMerge module will be used to expedite anatomical mapping using the MRI data collected.

- 5. The mapping catheter will be removed and an intracardiac echo (ICE) catheter, will be inserted through the femoral vein.
- 6. The conduction system pacing lead will be inserted through the axillary vein. A right atrial lead will be inserted into the right ventricular apex for back up pacing in the instance the conduction system is bumped. The basal-septum, mid-septum, high-septum and anterior walls will be paced to identify electrical markers for optimal implant sites.
- 7. The lead will be visualised on the Carto maps created.
- 8. The lead will be deployed at the predetermined target site under direct visualisation using the ICE catheter. Through direct visualisation, three key determinants can be assessed:
 - 1. Lead trajectory through the septum with the goal of achieving perpendicularity
 - Lead septum interaction and whether there is evidence of entanglement preventing lead progression.
 - Relationship between the sheath and lead that can lead to or prevent failure of lead deployment.
- 9. Once the conduction lead is secured the right atrial lead will be pulled back and secured in the right atrium.
- 10. The procedure will be completed as per standard clinical implant protocol with routine clinical follow-up thereafter:

The information from echocardiography will be corroborated with the lead-septum interaction visualised on electro-anatomical maps created on CARTO.

In this cohort of patients, the conduction system lead will initially pace the His-bundle then the left bundle in order to collect data for both methods of physiological pacing. The information collected from ICE and electro-anatomical mapping will be used to develop a streamlined workflow that will map targeted areas, where challenging implant sites will be rapidly identified (such as areas of scar), reducing the number of attempted lead deployments and visualise lead-septum interaction, apposition and progression, improving safety parameters.

At the end of the procedure, the lead position will be documented with a very short, *single fluoroscopic acquisition*. This remains integral for future comparison in the instances of lead complications and in particular lead displacement.

4.2 Validation

25 patients will be recruited to the validation cohort.

An optimised work flow will be derived using the information collected from the derivation cohort. Namely, the target areas for FAM and electro-anatomical maps will be determined, and the successful pattern of lead septum interaction on CARTO will be defined.

The streamlined workflow will then be applied to 25 prospective patients. The success rates, procedure time, fluoroscopy time, capture threshold, number of attempted lead deployments and complication rates will be assessed.

4.3 Control Arm

The control arm will consist of 25 patients undergoing a conduction system pacemaker using conventional pacing methods, with the same pacing indications as the study arm.

[figure not shown]

Figure 1: Recruitment workflow

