4.6 Study Outcome Measures

Primary Outcome Measures

1. Success rates of conduction system lead implant (fluoroless workflow vs conventional methods)

Secondary Outcome Measures

- Procedure and fluoroscopy times of the fluoroless workflow vs current conventional methods of His-bundle and Left-bundle pacing
- Procedure and fluoroscopy times of the fluoroless workflow vs conduction system implant to current right ventricular pacing
- 3. Assess capture threshold of His-bundle and Left-bundle pacing from the fluoroless workflow vs that of conventional methods of conduction system implantation
- 4. Number of times leads deployed in the fluoroless protocol vs conventional methods of conduction system implantation
- Complication rates in the fluoroless protocol vs conventional methods of conduction system implantation:

- a. Lead implanted at the incorrect position: non-septal positions
- b. Lead displacement
- c. Lead injury
- d. Rise in threshold (late complication)
- e. Vascular injury
- f. Perforation with or without subsequent tamponade
- g. Device related infection
- h. Pneumothorax

5 Participant Entry

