6.4 Serious AEs

An SAE form should be completed and faxed to the Chief Investigator within 24 hours. However, hospitalisations for elective treatment of a pre-existing condition do not need reporting as SAEs.

All SAEs should be reported to the "name of REC when allocated" where in the opinion of the Chief Investigator, the event was:

• 'related', ie resulted from the administration of any of the research procedures; and

• 'unexpected', ie an event that is not listed in the protocol as an expected occurrence

Reports of related and unexpected SAEs should be submitted within 15 days of the Chief Investigator becoming aware of the event, using the NRES SAE form for non-IMP studies. The Chief Investigator must also notify the Sponsor of all related and unexpected SAEs.

Local investigators should report any SAEs as required by their Local Research Ethics Committee, Sponsor and/or Research & Development Office.

Contact details for reporting SAEs

[contact]

[name] email: [contact]
Please send SAE forms to: [name].
[contact] (Mon to Fri 09.00 – 17.00)

7 Assessment and Follow-up

Patients will be followed up for a 1 year period. During this time they will undergo the device interrogation and wound check at 6 weeks as part of standard clinical care. One year after device implantation, patients will undergo a device interrogation follow-up appointment. Any incidental findings that we identify during the study will be reviewed by the research team and reported to the GP and also the cardiology team normally looking after the patient.

Definition of end of Study

The end of the study will be defined as completion of the 1 year follow-up of the 75 prospectively recruited patients for the invasive aspect of the study. This will be the date of the final visit of the last participant at 1 year.

8 Statistics and data analysis

The following statistical analysis has been reviewed and approved by our statistician, [name].

Power Calculations:

25 patients would provide the ability to determine the mean time of lead implantation of 120 minutes with a precision of (as a standard error) approximately \pm 10 minutes (assuming standard deviation of 47 min)⁷

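### The primary workflow-versus-conventional comparison has no stated allocation rule or enrolment window for controls, so case-mix, calendar time and operator experience can pass for a workflow effect

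*Protocol*

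**What the plan says.** The Study Summary labels the design "Cohort observational study and interventional at validation phase". Section 3 forms the mapped cohorts in one sentence: "The patients will be divided into two groups; 25 patients in the derivation cohort and 25 patients in the validation cohort". It gives no method of division. It then adds the comparator: "The 25 patients undergoing conventional methods of conduction system pacing will be recruited as a control arm to compare these outcomes".

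Section 4.2 sets the order of the mapped cohorts. The workflow is derived first, and then: "The streamlined workflow will then be applied to 25 prospective patients". Section 4.3 defines controls as patients "undergoing a conduction system pacemaker using conventional pacing methods, with the same pacing indications as the study arm". The primary outcome in section 4.6 is a contrast between groups: "Success rates of conduction system lead implant (fluoroless workflow vs conventional methods".

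On timing, the end-of-study definition in section 7 refers to "completion of the 1 year follow-up of the 75 prospectively recruited patients", so controls are prospective. Section 5.5 covers identification and consent and has no step that assigns a patient to a group. Section 4.1 requires operators with more than 40 prior leads, and sections 4.2 and 4.3 do not repeat this. Section 8 tests success rates with a t-test and states no adjustment for differences between groups.

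**The concern.** A difference in success between validation and control patients can be read as the effect of the workflow only if the groups would have had similar success under the same method. Shared indications do not secure that. Section 1.1 itself ties implant difficulty to septal fibrosis, chamber dilatation and lead trajectory ("The target area is smaller than conventional right ventricular pacing, and can be even smaller when there is fibrosis in the septum"). It also reports success from 95% in experienced centres down to 56% in centres with new implanters. Patients with the same indication can therefore differ widely in their chance of success, according to anatomy and operator.

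The readable text leaves three routes to imbalance open: which patients enter which group, when they are implanted, and who implants them. At stake are the primary outcome and Hypotheses 2 and 3 of section 1.2 (safety and procedure time), which depend on the same comparator.

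**Working it through.** **1. The plan's own figures.** Section 8 assumes 80% success with n = 25: SE = sqrt(0.8 × 0.2 / 25) = 0.080, the stated 8%. For implant time, SD = 67/√2 = 47.38 and SE = 47.38/√25 = 9.48 minutes (stated as 9.47). Both reproduce. Both describe one group.

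**2. The yardstick for a comparison.** With 25 per group and 80% success in each, SE of the difference = sqrt(2 × 0.8 × 0.2 / 25) = 0.113, or 11.3 points. The 95% half-width is 1.96 × 11.3 = 22.2 points.

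**3. What the readable text fixes for each group.**

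| Feature | Validation | Control |
|---|---|---|
| Pacing indication | As sections 3 and 5.2 | Same as study arm (4.3) |
| Eligibility | Section 5 | Section 5 |
| Prospective, same follow-up visits | Yes (4.4, 7) | Yes (4.4, 7) |
| Earliest start | After derivation (4.2) | Not stated |
| Operator experience | Not stated (4.1 covers derivation) | Not stated |
| How a patient enters the group | Not stated | Not stated |

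The first row is less firm than it looks. The Study Summary excludes patients with an indication for cardiac resynchronisation, while section 5.2 includes left bundle branch block for that therapy. The two lists must be reconciled before the same-indication condition has one meaning.

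**4. Illustration: anatomy.** All inputs are assumed. Success is 90% in easy and 50% in difficult anatomy, identical for both methods, so the workflow has no effect.

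- 20% difficult: 0.8 × 0.90 + 0.2 × 0.50 = 0.82
- 40% difficult: 0.6 × 0.90 + 0.4 × 0.50 = 0.74
- 10% difficult: 0.9 × 0.90 + 0.1 × 0.50 = 0.86

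Validation 20% versus control 40% gives 82% − 74% = 8 points, which is 8/11.3 = 0.7 SE of the difference. At 10% versus 40% it is 86% − 74% = 12 points, or 12/11.3 = 1.1 SE. Reversing the shares reverses the sign.

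**5. Illustration: operator experience.** Here 95% and 56% are the centre-experience figures in section 1.1; only the shares of procedures done in the experienced setting are assumed. Again the workflow has no effect.

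- 70% versus 50%: (0.70 × 0.95 + 0.30 × 0.56) − (0.50 × 0.95 + 0.50 × 0.56) = 0.833 − 0.755 = 7.8 points
- 80% versus 50%: 0.872 − 0.755 = 11.7 points

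By a normal approximation with 25 per group, the chance of a two-sided p < 0.05 rises from 5% to about 10% and 18% respectively.

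**The case against.** The strongest reply is that this is a feasibility study. The label is a cohort study, the aim is to define a workable protocol, and the sample size rests on single-group precision. A non-randomised control is an accepted choice in that setting. That stands as a defence of the design type. It does not cover a primary outcome worded as a contrast, with controls recruited for that purpose.

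The reply can also point to safeguards that do exist: one set of criteria in section 5, the same follow-up for all, and prospective recruitment of all 75. These stand, and they rule out a purely historical control. Prospective is not concurrent, however, and controls could still be implanted while derivation is under way. Figure 1, the recruitment workflow, may show an allocation step. The control-group fragment that survives in section 4.5 does not, but the figure could not be checked.

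A reader might go further and infer that the team steers patients after seeing their scans, or that sheaths and technique improve over the year. The documents support neither. No passage says who chooses the group. Imaging is listed before the procedure, not before assignment, and section 4.1 describes retrospective use of the MRI in derivation. Nothing reports a change in equipment. The point rests on the absence of a rule, not on evidence of selection.

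A separate analysis plan might add covariates. It could not restore concurrent enrolment or unbiased assignment.

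**Conclusion.** The concern holds in this form: subject to Figure 1, the protocol makes a between-group comparison primary without fixing how or when controls enter, or who implants them. The comparison is then open to confounding of unknown size and direction, and the stated t-test would attribute it to the workflow. Under the assumptions shown, modest to marked imbalance produces about 8 to 12 spurious points, which is 0.7 to 1.1 times the 11.3-point standard error of the difference. Measuring the bias against the 8% in section 8 would overstate it, because that is a one-group figure. The documents give no estimate of actual imbalance.

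It would be too strong to conclude that the study answers nothing. Hypothesis 1 (implantation with almost no fluoroscopy) and the single-group success estimate in validation patients do not need the control arm and are unaffected. This is a change that should be made, not a fatal flaw.

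**What to change.** Amend sections 3, 4.2 and 4.3. Once the workflow is fixed after derivation, recruit the remaining 50 patients as one consecutive series and randomise them 1:1, with concealed allocation, to the workflow (25) or conventional implantation (25).

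If the cohort design is kept:

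- enrol controls consecutively during the validation period and at the same sites;
- apply the same operator-experience requirement to validation and control procedures;
- set the group from a concealed list before imaging is reviewed (alternation is predictable and would leave steering possible);
- describe the comparison as non-randomised and exploratory.

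Cost: a protocol and consent amendment and an allocation list, with the same 75 patients and the same procedures. Controls could be enrolled only after all 25 derivation implants, which may lengthen recruitment, and patients must accept allocation. Randomising removes systematic bias but adds no power: with 25 per group, 80% versus 95% has about 36% power at two-sided 0.05.
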